### **Research Ethics Committees**

23. The research protocol must be submitted for consideration, comment, guidance and approval to the concerned research ethics committee before the study begins. This committee must be transparent in its functioning, must be independent of the researcher, the sponsor and any other undue influence and must be duly qualified. It must take into consideration the laws and regulations of the country or countries in which the research is to be performed as well as applicable international norms and

4/8

standards but these must not be allowed to reduce or eliminate any of the protections for research subjects set forth in this Declaration.

The committee must have the right to monitor ongoing studies. The researcher must provide monitoring information to the committee, especially information about any serious adverse events. No amendment to the protocol may be made without consideration and approval by the committee. After the end of the study, the researchers must submit a final report to the committee containing a summary of the study's findings and conclusions.

### **Privacy and Confidentiality**

24. Every precaution must be taken to protect the privacy of research subjects and the confidentiality of their personal information.

### **Informed Consent**

25. Participation by individuals capable of giving informed consent as subjects in medical research must be voluntary. Although it may be appropriate to consult family members or community leaders, no individual capable of giving informed consent may be enrolled in a research study unless he or she freely agrees.

26. In medical research involving human subjects capable of giving informed consent, each potential subject must be adequately informed of the aims, methods, sources of funding, any possible conflicts of interest, institutional affiliations of the researcher, the anticipated benefits and potential risks of the study and the discomfort it may entail, post-study provisions and any other relevant aspects of the study. The potential subject must be informed of the right to refuse to participate in the study or to withdraw consent to participate at any time without reprisal. Special attention should be given to the specific information needs of individual potential subjects as well as to the methods used to deliver the information.

After ensuring that the potential subject has understood the information, the physician or another appropriately qualified individual must then seek the potential subject's freely-given informed consent, preferably in writing. If the consent cannot be expressed in writing, the non-written consent must be formally documented and witnessed.

All medical research subjects should be given the option of being informed about the general outcome and results of the study.

27. When seeking informed consent for participation in a research study the physician must be particularly cautious if the potential subject is in a dependent relationship with the physician or may consent under duress. In such situations the informed consent must be sought by an appropriately qualified individual who is completely independent of this relationship.
28. For a potential research subject who is incapable of giving informed consent, the physician must seek informed consent from the legally authorised representative. These individuals must not be included in a research study that has no likelihood of benefit for them unless it is intended to promote the health of the group represented by the potential subject, the research cannot instead be performed with persons capable of providing informed consent, and the research entails only minimal risk and minimal burden.
29. When a potential research subject who is deemed incapable of giving informed consent is able to give assent to decisions about participation in research, the physician must seek that assent in addition to the consent of the legally authorised representative. The potential subject's dissent should be respected.
30. Research involving subjects who are physically or mentally incapable of giving consent, for example, unconscious patients, may be done only if the physical or mental condition that prevents giving informed consent is a necessary characteristic of the research group. In such circumstances the physician must seek informed consent from the legally authorised representative. If no such representative is available and if the research cannot be delayed, the study may proceed without informed consent provided that the specific reasons for involving subjects with a condition that renders them unable to give informed consent have been stated in the research protocol and the study has been approved by a research ethics committee. Consent to remain in the research must be obtained as soon as possible from the subject or a legally authorised representative.
31. The physician must fully inform the patient which aspects of their care are related to the research. The refusal of a patient to participate in a study or the patient's decision to withdraw from the study must never adversely affect the patient-physician relationship.
32. For medical research using identifiable human material or data, such as research on material or data contained in biobanks or similar repositories, physicians must seek informed consent for its collection, storage and/or reuse. There may be exceptional situations where consent would be impossible or impracticable to obtain

for such research. In such situations the research may be done only after consideration and approval of a research ethics committee.

### **Use of Placebo**

33. The benefits, risks, burdens and effectiveness of a new intervention must be tested against those of the best proven intervention(s), except in the following circumstances:

Where no proven intervention exists, the use of placebo, or no intervention, is acceptable; or

Where for compelling and scientifically sound methodological reasons the use of any intervention less effective than the best proven one, the use of placebo, or no intervention is necessary to determine the efficacy or safety of an intervention

and the patients who receive any intervention less effective than the best proven one, placebo, or no intervention will not be subject to additional risks of serious or irreversible harm as a result of not receiving the best proven intervention.

Extreme care must be taken to avoid abuse of this option.

### **Post-Trial Provisions**

34. In advance of a clinical trial, sponsors, researchers and host country governments should make provisions for post-trial access for all participants who still need an intervention identified as beneficial in the trial. This information must also be disclosed to participants during the informed consent process.

### **Research Registration and Publication and Dissemination of Results**

35. Every research study involving human subjects must be registered in a publicly accessible database before recruitment of the first subject.

36. Researchers, authors, sponsors, editors and publishers all have ethical obligations with regard to the publication and dissemination of the results of research. Researchers have a duty to make publicly available the results of their research on human subjects and are accountable for the completeness and accuracy of their reports. All parties should adhere to accepted guidelines for ethical reporting. Negative and inconclusive as well as positive results must be published or otherwise made

7/8

publicly available. Sources of funding, institutional affiliations and conflicts of interest must be declared in the publication. Reports of research not in accordance with the principles of this Declaration should not be accepted for publication.

### **Unproven Interventions in Clinical Practice**

37. In the treatment of an individual patient, where proven interventions do not exist or other known interventions have been ineffective, the physician, after seeking expert advice, with informed consent from the patient or a legally authorised representative, may use an unproven intervention if in the physician's judgement it offers hope of saving life, re-establishing health or alleviating suffering. This intervention should subsequently be made the object of research, designed to evaluate its safety and efficacy. In all cases, new information must be recorded and, where appropriate, made publicly available.

© World Medical Association, Inc. - All Rights reserved.  
© Asociación médica mundial - Todos los derechos reservados.  
© L'Association Médicale Mondiale - Tous droits réservés.

FOP-PFQ	FOP-Physical Function Questionnaire
GEE	generalized estimating equation
HO	heterotopic ossification
ICH	International Council for Harmonisation
MedDRA	Medical Dictionary for Regulatory Activities
NHS	Natural History Study
PAS	Pharmacokinetic Analysis Set
PK	pharmacokinetic(s)
PPC	Premature physelial closure
PPS	Per Protocol Set
PROMIS	Patient Reported Outcomes Measurement Information System
ROM	Range of motion
SAE	serious adverse event
SAS	Safety Analysis Set
SAP	statistical analysis plan
SD	standard deviation
T _{max}	time to maximum plasma concentration
WBCT	whole body computed tomography
wLME	weighted linear mixed effect

1 OVERVIEW AND INVESTIGATIONAL PLAN

1.1 Context for Version 1.3.1

This amendment is introduced to make several clarifications in preparation for the writing of the final CSR.

1.2 Context for Version 1.3

This amendment is introduced in preparation for the writing of the final CSR.

1.3 Context for Version 1.2

This amendment is introduced after the third interim analysis. It introduces edits, including changes to existing analyses and additions of new analyses, to be included in the interim CSR for Study PVO-1A-301 (MOVE Trial) to be included in the palovarotene marketing authorization application for FOP.

1.4 Context for Version 1.1

This amendment is introduced after the second interim analysis but before the planned third interim analysis (anticipated to be held in mid-May 2020). The futility boundary was crossed at the second interim analysis, signifying that the prespecified Bayesian compound Poisson distribution model with square-root transformation indicated that the trial was unlikely to show sufficient evidence of benefit. The independent data monitoring committee (DMC) informed the sponsor of this outcome on January 15, 2020, and the efficacy assessments were subsequently unblinded to the sponsor.

Based on additional post-hoc analyses presented to the DMC on January 21, 2020, the DMC noted that using the square-root transformation of the data in the primary analysis appears to have moved the statistical conclusion from significant therapeutic benefit to showing futility of the treatment. The DMC also noted that the dilemma created by these highly disparate results precludes a confident conclusion about futility. As such, the DMC recommended that additional analyses be conducted and provided to them for consideration at the next interim analysis.

US FDA instituted a partial clinical hold on dosing of palovarotene due to premature physcal closure (PPC) for subjects <14 years of age on December 4, 2019; as of the finalization of this SAP amendment, dosing has not yet resumed for these subjects. Dosing on all other subjects not subject to US FDA's partial clinical hold was interrupted following the January 21, 2020 DMC meeting while the protocol amendment allowing the continuation of the study after the futility outcome and incorporating the additional analyses requested by the DMC was reviewed by regulatory agencies, IRBs, and investigational sites. These subjects had palovarotene dosing interrupted on or around January 24, 2020. The sponsor allowed dosing to resume as of March 26, 2020, provided each individual site had obtained Ethics Committee approval to do so and the site was able to fulfil regulatory and operational requirements. Subjects were expected to restart dosing over a span of weeks due to these logistical considerations.

Note that Sections 1.3 (Study design), 1.4 (Objectives), 1.5 (Determination of sample size) and 1.6 (Study plan) were unchanged from the SAP V1.0, which was finalized prior to the first

interim analysis. New content began in Section 1.7 (Modifications to the statistical section of the protocol).

1.5 Study Design

Study PVO-1A-301 (referred to as the MOVE Trial) is a Phase 3, multicenter, open-label study in adult and pediatric subjects with fibrodysplasia ossificans progressiva (FOP) which will be conducted in three parts: Part A, the main part of the study; Part B, the 24-month extension and Part C, the up-to-2 year post-treatment period for skeletally immature subjects. Sources of subjects eligible for enrollment in the MOVE Trial include: (1) subjects from Study PVO-1A-001 (natural history study [NHS]); (2) additional subjects clinically diagnosed with FOP with the R206H ACVR1 mutation or other FOP variants reported to be associated with progressive heterotopic ossification (HO) (who have not previously participated in any Clementia-sponsored study); and (3) subjects in Study PVO-1A-202 or Study PVO-1A-204 who cannot receive the chronic/flare-up regimen due to country of residence or those traveling long distances to participate in the Phase 2 trial. Approximately 110 subjects will be enrolled into the MOVE Trial (approximately 99 with the R206H mutation and no previous exposure to palovarotene, and approximately 11 with other mutations or previous participation in the Phase 2 trials) In Part A, qualified subjects will receive chronic dosing with palovarotene for up to 24 months and undergo flare-up treatment should they experience an eligible flare-up or traumatic event.

Part C was added for skeletally immature subjects who stopped taking study medication for any reason before completion of Part A/B. Part C includes yearly visits for up to a 2-year follow-up period following last dose. No dosing will occur during Part C. Assessments obtained in Part C include yearly linear height, knee height, weight, physical exam, vital signs, radiographic assessments of the knee and hand-wrist, low-dose WBCT imaging excluding head, adverse events, and concomitant medications. Participation in Part C will continue only as long as subjects remain skeletally immature. The up to 2-year period for Part C would begin the last day the subject stopped receiving study drug in Part A/B. However, the maximum participation in the trial will not be extended beyond 48 months for Parts A, B, and C in total. Secondary objective added for Part C to monitor off treatment longer-term safety in skeletally immature subjects off treatment.

This is an open-label study, with the comparator arm being subject data from the NHS. The efficacy of palovarotene treatment in the MOVE Trial, as measured by the change in new HO volume (the primary efficacy endpoint), will be compared to that observed in untreated subjects who participated in the NHS.

As of 04Dec2019 all subjects <14 years of age were required to interrupt study drug due to a partial clinical hold placed on the palovarotene clinical development program by the US FDA. Treatment will subsequently not be restarted in children <14 years of age.

There are three formal interim efficacy analyses and a final analysis planned; an additional descriptive analysis occurred before the first formal interim efficacy analysis to be included in the then-planned marketing authorization filing for episodic palovarotene prevention of HO in patients with FOP. The interim efficacy analyses will be conducted to assess whether efficacy of

the chronic/flare-up regimen is sufficiently demonstrated prior to the completion of the study. The study will not stop early if an interim efficacy analysis meets the efficacy criteria (pre-specified to trigger potential early submission for marketing authorization); subjects will continue treatment until completion of two years of palovarotene treatment.

A futility analysis will be conducted at the second and third interim analyses to assess whether the study should be stopped due to insufficient evidence of efficacy.

The statistical analyses and summary tabulations described in this Statistical Analysis Plan (SAP) will provide the basis for the results sections of the MOVE clinical study reports.

1.6 Objectives

1.6.1 Primary Objectives

- To evaluate the efficacy of palovarotene in decreasing heterotopic ossification (HO) in adult and pediatric subjects with FOP as assessed by low-dose, whole body computed tomography (WBCT), excluding head, as compared to untreated subjects from Clementia's FOP natural history study over 24 months.
- To evaluate the safety of palovarotene in adult and pediatric subjects with FOP.

1.6.2 Secondary Objectives

- To evaluate the effect of palovarotene on flare-up rate and proportion of subjects reporting at least one flare-up.
- To evaluate the effect of palovarotene on range of motion (ROM) as assessed by the Cumulative Analogue Joint Involvement Scale (CAJIS) for FOP.
- To evaluate the effect of palovarotene on physical function using age appropriate forms of the FOP Physical Function Questionnaire (FOP-PFQ).
- To evaluate the effect of palovarotene on physical and mental health using age-appropriate forms of the Patient Reported Outcomes Measurement Information System (PROMIS) Global Health Scale.
- To evaluate the pharmacokinetics of palovarotene.
- Part B: To continue to provide palovarotene to adult and pediatric subjects with FOP and to monitor longer-term safety.
- Part C: To implement safety measures in order to ensure that assessments of safety continue for up to 2 years post last dose of study treatment for skeletally immature subjects.

1.7 Determination of Sample Size

The sample size required for the MOVE Trial was determined via simulation based on the available WBCT HO volumes from the NHS and the observed efficacy of palovarotene treatment in Phase 2. The NHS will serve as the external control group with, for the purposes of the determination of sample size, the assumption that 45 subjects will have baseline, 1-year, and 1.5-year WBCT HO volumes and 45 subjects will have baseline, 1-year, and 2-year WBCT HO volumes. It is also assumed that approximately 50% of these 90 subjects will enter the Phase 3 study to begin palovarotene treatment.

There are three interim efficacy analyses – with futility analyses at the second and third interim analyses – and a final analysis planned. Assuming a one-sided, overall type I error rate of 2.5%, the Lan-DeMets alpha-spending function with O’Brien-Fleming parameterization was used to determine stopping boundaries (see [Section 0](#) for additional details).

Available pairs of NHS WBCT scans for 65 subjects taken one year apart and read using the original NHS single-reader process were used to tabulate the number of body regions with new HO and the mean and standard deviation (SD) of new HO volume in each body region ([Table 1](#)). The original 15 body regions from the NHS WBCT scans were mapped to approximate the 9 body regions that will be used in the MOVE Trial. The mean (SD) number of body regions with new HO per subject in approximately one year was 0.707 (1.11), i.e., there were 46 body regions with new HO in 65 subjects.

Table 1. NHS WBCT Scan Results by Body Region

Body region	Number of observations	Number of regions with new NO	Proportion of regions with new HO	Volume change given new HO in region (in thousands mm ³)	
				Mean	SD
Neck, upper spine and chest	64	12	0.19	25.83	21.06
Shoulder (left, right)	130	7	0.05	4.69	3.08
Elbow, hand and wrist (left, right)	125	1	0.01	31.27	-
Lower spine and abdomen	65	11	0.17	16.22	19.24
Hip (left, right)	130	9	0.07	81.17	89.65
Knee and distal lower extremity (left, right)	128	6	0.05	9.04	14.64

Simulations to assess power were conducted as follows:

1. A subject-level rate of body regions with new HO were randomly drawn from a gamma distribution with mean = 0.707 and SD = 1.11.
2. Using the subject-level rate, the numbers of regions with new HO for each WBCT scan were simulated using a Poisson distribution. The rate was scaled to the duration of time between each WBCT scan and the previous WBCT scan.

3. Given the number of regions with new HO, the specific body regions with new HO were randomly selected assuming equal probability across regions.
4. For each body region with new HO, the increase in HO volume was simulated from a gamma distribution parameterized with the mean and SD in [Table 1](#).
 - a. For the elbow, hand and wrist (left, right), the SD was assumed to be equal to the mean.
5. The resulting dataset was analyzed as described in [Section 0](#) at the scheduled analysis time points.

Note that drawing subject-level rates of body regions with new HO from a gamma distribution and then drawing from Poisson distributions using these subject-level rates implies that the marginal distribution of the number of body regions with new HO follows a negative binomial distribution, which requires much less restrictive assumptions than a Poisson distribution and does not tend to result in an underestimate of the variance.

The simulated power is summarized in [Table 2](#) given the specified testing sequence, 80 subjects enrolled into the MOVE Trial with the R206H mutation and no previous palovarotene experience (including approximately 45 subjects from the NHS) and the NHS serving as the external control group with 45 subjects with baseline, 1-year and 1.5-year WBCT HO volumes and 45 subjects with baseline, 1-year and 2-year WBCT HO volumes; it is assumed that the full NHS dataset will be available at the first interim analysis.

Table 2. Power of MOVE Study Primary Efficacy Analysis Assuming 80 Subjects Enrolled with the R206H Mutation and No Previous Palovarotene Exposure

Scenario		Cumulative Probability of Success			
% Reduction HO Volume Conditional on New HO in a Body Region	% Reduction in Number of Regions with New HO	Interim #1	Interim #2	Interim #3	Final
0%	0%	0.006	0.010	0.013	0.021
50%	30%	0.507	0.789	0.886	0.922

The primary efficacy analysis comparing the annualized change in new HO volume between subjects treated with palovarotene and untreated subjects has an overall probability of study success of 0.92 if palovarotene treatment reduces the number of regions with new HO by 30% and reduces the volume of new HO conditional on new HO in a per body region by 50%. With this treatment effect, the probability of declaring study success is 0.51, 0.79, and 0.89 at the first, second, and third interim analyses, respectively. [Table 2](#) shows that the type I error rate is maintained under the null hypothesis of no palovarotene treatment effect.

Note that Protocol Amendment 2 increased the number of subjects enrolled from approximately 90 to a maximum of 110 (up to 99 with the R206H mutation and no previous exposure to palovarotene; up to 11 with other mutations and previous participation in the Phase 2 trials). This

increase in the number of enrolled subjects, implemented late in enrollment to allow sites to screen already-scheduled patients and enroll those found to be eligible, does not substantially change the power of the trial or have a significant impact on the primary or secondary statistical analyses.

Additional details of the operating characteristics of the Bayesian analysis including its chance of producing erroneous conclusions and the reliability of treatment effect estimates will be included in a separate simulation report, which will be included in the interim clinical study report as an appendix.

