### 8.2 Sample Size Determination

The sample size required for this Phase 3 study was determined via simulation based on the available WBCT HO volumes from the NHS and the observed efficacy of palovarotene treatment in the Phase 2 studies. The NHS will serve as the external control group, with the expectation that 45 subjects will have baseline, 1-year, and 1.5-year WBCT HO volumes and 45 subjects will have baseline, 1-year, and 2-year WBCT HO volumes. It is also anticipated that approximately 50% of these 90 subjects will enter the Phase 3 study to begin palovarotene treatment.

There are three interim efficacy analyses and a final analysis planned. Assuming a one-sided, overall type I error rate of 2.5%, the Lan-DeMets alpha-spending function with O'Brien-Fleming parameterization was used to determine stopping boundaries (see Section 8.5.2 for additional details). The simulated power is summarized in Table 6, given the specified testing sequence and 80 subjects originally planned for enrollment into the current study with the R206I mutation and no previous palovarotene experience (including approximately 45 subjects from the NHS). Note that the increase in the number of enrolled subjects will not substantially change the power of the trial or have a significant impact on the primary or secondary statistical analyses.

**Table 6. Power of MOVE Study Primary Efficacy Analysis Assuming 80 Subjects Enrolled with the R206H Mutation and No Previous Palovarotene Exposure**

Scenario		Cumulative Prob. of Success			
% Reduction HO Volume Conditional on New HO in a Body Region	% Reduction in Number of Regions with New HO	Interim #1	Interim #2	Interim # 3	Final
0%	0%	0.006	0.010	0.013	0.021
50%	30%	0.507	0.789	0.886	0.922

HO=heterotopic ossification.

The primary efficacy analysis comparing the annualized change in new HO volume between subjects treated with palovarotene and untreated subjects has an overall probability of study success of 0.92 if palovarotene treatment reduces the number of regions with new HO by 30% and reduces the new HO volume conditional on new HO in a per body region by 50%. With this treatment effect, the probability of declaring study success is 0.51, 0.79, and 0.89 at the first, second, and third interim analyses, respectively. Table 6 shows that the type I error rate is maintained under the null hypothesis of no palovarotene treatment effect.

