1.9 Modifications to the Statistical Section of the Protocol

1.9.1 Modifications to the Statistical Section of Protocol Amendment #1

The method for the primary efficacy analysis (a Bayesian analysis of a compound Poisson distribution) described in Protocol Amendment 1 and this SAP is different from the method included in the original protocol dated 10 July 2017 (weighted linear mixed effects model). The method and accompanying power simulations in the original protocol were based on a March 2017 evaluation of the available NHS 12-month WBCT data. In a subsequent dataset, increased variability in the change from baseline in new HO resulted in a substantive power decrease for the weighted linear mixed effects model. Therefore, additional modeling and simulation work was undertaken to assess whether alternative models or transformations would be more appropriate methods of analyzing the data, and thus maintain the power of the MOVE Trial. This resulted in changes to the primary efficacy analysis method as well as the simulations underlying sample size determination. Additionally, the Lan-DeMets alpha-spending function with Pocock parameterization was revised to O'Brien-Fleming parameterization based on FDA scientific advice.

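### The power simulation in SAP 1.7 gives the subject-level rate the SD of the observed counts, so Poisson variance enters twice: as written, simulated one-year counts have SD 1.39 against 1.11 in the NHS

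*SAP*

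**What the plan says.** SAP 1.7 describes the NHS data behind the simulation: "The mean (SD) number of body regions with new HO per subject in approximately one year was 0.707 (1.11"), that is, 46 regions in 65 subjects. Step 1 then states: "A subject-level rate of body regions with new HO were randomly drawn from a gamma distribution with mean = 0.707 and SD = 1.11". In step 2, "the numbers of regions with new HO for each WBCT scan were simulated using a Poisson distribution", with the rate scaled to the interval between scans. A note after the steps says that the resulting counts are marginally negative binomial, which "requires much less restrictive assumptions than a Poisson distribution and does not tend to result in an underestimate of the variance".

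The resulting power appears in SAP Table 2 and again in protocol Table 6 (Protocol 8.2): 0.507, 0.789, 0.886 and 0.922 at the three interims and the final analysis, for 30% fewer regions with new HO and 50% less volume per affected region. The SAP text says the primary analysis "has an overall probability of study success of 0.92" under that effect. Protocol 8.2 repeats the interim figures: "With this treatment effect, the probability of declaring study success is 0.51, 0.79, and 0.89". SAP 1.7 leaves further detail to a separate report: "Additional details of the operating characteristics of the Bayesian analysis including its chance of producing erroneous conclusions". SAP 1.9.1 explains that the first primary method lost power on later NHS data and that alternatives were sought to maintain it: "This resulted in changes to the primary efficacy analysis method as well as the simulations underlying sample size determination".

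**The concern.** The figure 1.11 describes counts, but step 1 uses it for a latent rate. In a gamma-Poisson model the variance of the counts is the mean plus the variance of the rate. A count SD therefore cannot be passed to the gamma distribution unchanged; the Poisson part has to be removed first. Nothing in SAP 1.7 does this, and nothing presents 1.11 as a deliberately conservative choice. The note about not underestimating variance only contrasts the model with a plain Poisson.

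What is at stake is the correctness of a headline design figure. Both power tables are said to rest on the NHS volumes. Someone who follows step 1 simulates a more variable population than the NHS sample, and cannot tell whether 0.92 belongs to that population or to one that matches the NHS. The figure also supports the change of primary method described in SAP 1.9.1.

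**Working it through.** **Inputs from SAP 1.7.** Mean count 0.707 (46/65 = 0.708; the SAP Table 1 counts 12 + 7 + 1 + 11 + 9 + 6 sum to 46). Count SD 1.11, variance 1.11² = 1.2321.

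**Moments over one year.** If the rate has mean m and SD s, and the count is Poisson given the rate, then Var(count) = m + s².

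- As written, s = 1.11: variance 0.707 + 1.2321 = 1.9391, SD 1.3925. Relative to the NHS, the variance ratio is 1.9391/1.2321 = 1.57 and the SD ratio 1.3925/1.11 = 1.25. The gamma shape is 0.707²/1.2321 = 0.406, and the probability of no new HO in a year is 0.66.
- Matched to the NHS, s² = 1.2321 − 0.707 = 0.5251, so s = 0.725. The gamma shape is 0.952, and the probability of no new HO is 0.59.

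**Effect on power.** The simulation was rebuilt with 90 NHS subjects (45 with 1.5 years, 45 with 2 years), 80 MOVE subjects of whom 45 come from the NHS, six-monthly MOVE scans, looks as in SAP Table 7, and gamma volumes from SAP Table 1. Success was P(γ<1) above 1 minus 0.0058, 0.0103, 0.0156 and 0.0190. Rebuilds A and B are separate implementations of the Bayesian model on the square-root scale with the SAP 2.4.4 priors and no age or sex covariates. A used 2,000 trials per scenario and B used 1,100. C replaces the posterior with a normal approximation (3,000 trials).

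| | Interim 1 | Interim 2 | Interim 3 | Final |
|---|---|---|---|---|
| Stated | 0.507 | 0.789 | 0.886 | 0.922 |
| A, rate SD 1.11 | 0.453 | 0.717 | 0.848 | 0.889 |
| A, rate SD 0.725 | 0.526 | 0.795 | 0.898 | 0.932 |
| B, rate SD 1.11 | 0.442 | 0.722 | 0.843 | 0.888 |
| B, rate SD 0.725 | 0.554 | 0.794 | 0.898 | 0.928 |
| C, rate SD 1.11 | 0.533 | 0.786 | 0.890 | 0.923 |
| C, rate SD 0.725 | 0.577 | 0.841 | 0.932 | 0.955 |

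The Monte Carlo standard error at the final look is under 1 point in A and about 0.9 points in B.

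The gain from 1.11 to 0.725, in points at the four looks, is:

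- A: 7, 8, 5 and 4
- B: 11, 7, 6 and 4
- C: 4, 6, 4 and 3
- A with volumes scaled as sqrt(Z/1000), 1,000 trials: 10, 11, 8 and 6 (final 0.872 to 0.930)
- A with NHS crossovers enrolled first, 1,000 trials: 5, 6, 4 and 4 (final 0.893 to 0.935)

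**Which input produced the stated table?** With 1.11, A and B fall 3 to 7 points short at every look. With 0.725, A is within 2 points throughout, and B is too except at interim 1 (0.554 against 0.507). C instead matches the stated table with 1.11, within half a point at the last three looks. The stated figures therefore do not settle which SD was used.

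**Null row.** In A, with 3,000 trials each, cumulative success under no effect is 0.003/0.007/0.012/0.016 with 1.11 and 0.005/0.009/0.015/0.019 with 0.725, against the stated 0.006/0.010/0.013/0.021. A run of only 300 trials in B with 1.11 gave 0.040 at the final look (standard error sqrt(0.04 × 0.96/300) = 0.011). That is too imprecise to set against the larger runs.

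**The case against.** The best defence is that step 1 discloses its input. Table 2 is then simply the power of that recipe, and the SAP never promises that simulated counts will have SD 1.11. The target is also noisy. In simulated samples of 65 from the matched model, 95% of sample SDs lie between 0.75 and 1.53, a range that includes 1.39. If the true count SD were 1.39, a sample SD of 1.11 or less would still occur in 24% of samples, or about 7% when the sample mean is close to 0.71. The rebuilds rest on unstated choices: the split of NHS crossovers, ten region slots taken from SAP Table 1 where the text speaks of nine regions, and no covariates. Finally, little now depends on the figure. Enrolment is complete at 99 in the principal population, the success and futility thresholds were dropped after the second interim (SAP 2.4.4), and the third interim is designated the final efficacy analysis.

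Most of this bears on importance, not correctness. Sampling error in 1.11 could justify a deliberately wider scenario, but the SAP would have to say so and give its implied count SD. The rebuild assumptions limit how precisely the power difference can be stated; the 1.39 needs no rebuild. The lost thresholds do reduce the practical weight. Even so, SAP 1.10.3 shows that this simulation text was revisited after the third interim, and the simulation report is to be appended to the interim CSR that goes into the marketing applications (SAP 1.7 and 3.3).

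**Conclusion.** The point holds. As written, steps 1 and 2 generate one-year counts with SD 1.39 instead of the NHS 1.11, a variance 57% too large; this is exact. It follows that either step 1 misdescribes the program, or the power in SAP Table 2 and protocol Table 6 is understated for the NHS variability it is said to reflect. The documents do not show which.

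The size of any understatement is about 3 to 6 points at the final analysis and 4 to 11 at the interims, conditional on the rebuild assumptions and on 0.725 as a point estimate from 65 subjects. The error runs in the conservative direction. It does not undermine the sample size, and the 3,000-trial null runs stay below 0.025. It is a matter of reporting the design correctly.

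**What to change.** State which SD parameterised the gamma rate.

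- **If 0.725 (variance 0.525) was used:** correct the SD in step 1 and leave the tables as they are.
- **If 1.11 was used:** re-run with 0.725 and restate SAP Table 2, protocol Table 6 (including the null row) and the matching sentences. The 1.11 run may stay as a scenario labelled conservative, with its implied count SD of 1.39.

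In both cases leave the equal-probability choice of regions unchanged and give the same input in the separate simulation report.

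The first branch costs one sentence. The second costs a re-run of an existing program and the replacement of two tables with their text; the protocol part would need an amendment under Protocol 9.2.5. Enrolment and all analyses are unaffected.
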